## **11.8 Sponsor's Reporting Responsibilities**

Serious and unexpected suspected adverse reactions (SUSARs) as defined in 21 CFR 312.32 and determined by the IND Sponsor will be reported to FDA and all participating Investigators as IND Safety Reports.

The IND Sponsor will also submit an IND Annual Report of the progress of the investigation to the FDA as defined in 21 CFR 312.33.

## **11.9 Halting Rules for the Protocol**

Halting the study requires immediate discontinuation of study agent administered for all subjects and suspension of enrollment until a decision is made whether or not to continue study agent administration.

The halting criteria (as determined by the site investigators) for an individual site include:

- Two or more subjects experience the same or similar SAEs that are unexpected and are possibly, probably, or definitely related to the study agent
- OR
- any safety issue that the site investigators determine should halt the study

The IRB/EC, the IND Sponsor, the DSMB or the FDA may halt the study at any time following review of any safety concerns

### **11.9.1 Reporting of Study Halting**

If a halting requirement is met, a description of the event(s) or safety issue must be reported by the PI within one business day to the Sponsor CSO, DSMB, and AstraZeneca by fax or email. The PI must also inform the IRB that a halting rule has been met.

### **11.9.2 Resumption of a Halted Study**

The IND Sponsor, in collaboration with the PI and DSMB will determine if it is safe to resume the study. The IND Sponsor will notify the PI of this decision. The conditions for resumption of the study will be defined in this notification. The PI will notify the IRB and AstraZeneca of the decision to resume the study.

## **11.10 Pausing Criteria for a Subject or Group**

The decision to suspend administration of the study agent(s) for a single subject or for all subjects in a specific group requires discontinuation of study agent administered for

the study subject(s) or group until a decision is made whether or not to continue study agent administration.

The pausing criteria for a single subject or for the subjects in a specific group in this study include:

- A subject experiences an SAE or Grade 3 or greater AE that is unexpected (as determined by the IND Sponsor) and is possibly, probably, or definitely related to the study agent;
- OR
- Any safety issue that the Site Investigator determines should pause administration of the study agent to a single subject or to all subjects in a specific group.

The IND Sponsor, in collaboration with the PI, may also pause for an individual subject or entire group if a safety concern is identified during routine aggregate data analysis.

#### **11.10.1 Reporting of Pausing for a Subject or Group**

If a pausing requirement is met, a description of the adverse event(s) or safety issue must be reported by the PI by fax or email within one business day to the Sponsor CSO, the IRB, the DSMB, and AstraZeneca.

#### **11.10.2 Resumption of a Paused Study**

The IND Sponsor in collaboration with the PI and DSMB will determine if it is safe to resume administration of the study agent to the subject/group. The IND Sponsor will notify the PI of this decision. The PI will notify the IRB and AstraZeneca of the decision to resume administration of the study agent prior to resumption.

### **11.11 Withdrawal Criteria for an Individual Subject**

An individual subject will be withdrawn for any of the following:

- An individual subject's decision.  
(The Investigator should attempt to determine the reason for the subject's decision.)
- Non-compliance with study procedures to the extent that it is potentially harmful to the subject or to the integrity of the study data.
- A change in the subject's baseline condition after enrollment so that the subject no longer meets the following exclusion criteria.
  - Malignancy (other than a resectable skin cancer)
  - HIV infection or any other known immunodeficiency.
  - Hepatitis B or C infection
  - Positive test for *FIP1L1/PDGFR* fusion gene
  - Suspicion of drug or alcohol abuse
  - Treatment with another investigational agent

## **11.12 Replacement of a Subject Who Discontinues Study Treatment**

Subjects who discontinue study treatment after the first dose will not be replaced.

## **11.13 Unblinding of the study**

### **11.13.1 Scheduled unblinding**

The study drug assignments will be unblinded after all 20 subjects have enrolled and completed the 13 week visit. At that time, efficacy and safety data collected through this time point will be analyzed.

### **11.13.2 Intentional Unscheduled Unblinding for Treatment Conditions**

Prior to breaking the treatment blind, the PI will be consulted. The research pharmacist will keep the treatment code list locked in a secure area and can be reached 24 hours a day to rapidly access subject unblinding codes if necessary. If a subject's treatment assignment is unblinded, the information will be provided only to the individuals needing it for treatment decisions, with documentation of the event and the reason for unblinding recorded in the subject's research record.

### **11.13.3 Reporting of Unblinding**

The PI must report all cases of unblinding (whether intentional or unintentional) in writing to the IRB, DSMB and AstraZeneca within 2 business days after the unblinding. If a serious adverse event (SAE) has resulted in unblinding, this information will be included in the SERF. Incidences of unblinding in and of themselves will be reported to the OCRPRO Clinical Safety Office. A detailed report of the event that resulted in the unblinding will be sent to the DSMB, AstraZeneca and the IRB.

## **11.14 Safety Oversight**

### **11.14.1 Safety Review and Communications Plan (SRCP)**

A Safety Review and Communication Plan (SRCP) has been developed for the protocol. The SRCP is an internal communications document between the PI and the CSO, which delineates the safety oversight responsibilities of the PI, the CSO, and other stakeholders. The SRCP also includes the overall plan for conducting periodic safety surveillance assessments.

### **11.14.2 Sponsor Medical Monitor (SMM)**

A Medical Monitor, representing the IND Sponsor (OCRPRO), has been appointed for oversight of safety in this clinical study. The Sponsor Medical Monitor will be

responsible for performing safety assessments as outlined in a Safety Review and Communications Plan (SRCP).

#### **11.14.3 Data and Safety Monitoring Board (DSMB)**

The NIAID Intramural DSMB will review the study prior to initiation and twice a year thereafter. The Board may convene additional reviews as necessary. The Board will review the study data to evaluate the safety, efficacy, study progress, and conduct of the study. All serious adverse events, all unanticipated problems, and all IND Safety Reports will be reported by the PI to the DSMB at the same time they are submitted to the IRB or IND Sponsor. The PI will notify the DSMB of any cases of intentional or unintentional unblinding as soon as possible. The PI will notify the Board at the time pausing or halting criteria are met and obtain a recommendation concerning continuation, modification, or termination of the study. The PI will submit the written DSMB summary reports with recommendations to the IRB.

#### **11.14.4 Unblinded Pathologist**

An NIH pathologist who is not involved in the clinical care of the study subjects will review all blinded CBCs and differentials obtained during the placebo-controlled portion of the study within 24 hours of the blood draw. Significant abnormalities (i.e., laboratory values that meet criteria for a grade 3 or 4 AE, SAE or that the pathologist deems clinically significant), will be reported to the PI and study coordinator immediately. Other laboratory abnormalities that represent grade 1 or 2 AEs and require no specific medical intervention, with the exception of the absolute eosinophil counts, will be reported to the PI and study coordinator in a weekly summary table.

## **12 Clinical Monitoring Structure**

### **12.1 Site Monitoring Plan**

As per ICH-GCP 5.18 and FDA 21 CFR 312.50, clinical protocols are required to be adequately monitored by the study sponsor. This study monitoring will be conducted according to the "NIAID Intramural Clinical Monitoring Guidelines. Monitors under contract to the NIAID/OCRPRO will visit the clinical research site to monitor aspects of the study in accordance with the appropriate regulations and the approved protocol. The objectives of a monitoring visit will be: 1) to verify the existence of signed informed consent documents and documentation of the ICF process for each monitored subject; 2) to verify the prompt and accurate recording of all monitored data points, and prompt reporting of all SAEs; 3) to compare CRIMSON data abstracts with individual subjects' records and source documents (subjects' charts, laboratory analyses and test results, physicians' progress notes, nurses' notes, and any other relevant original subject information); and 4) to help ensure investigators' are in compliance with the protocol. The monitors also will inspect the clinical site regulatory files to ensure that regulatory requirements (Office for Human Research Protections-OHRP), *FDA*, and applicable

guidelines (ICH-GCP) are being followed. During the monitoring visits, the investigator (and/or designee) and other study personnel will be available to discuss the study progress and monitoring visit.

The investigator (and/or designee) will make study documents (e.g., consent forms, CRIMSON data abstracts and pertinent hospital or clinical records) readily available for inspection by the local IRB, the FDA, the site monitors, and the NIAID staff for confirmation of the study data.

A specific protocol monitoring plan will be discussed with the Principal Investigator and study staff prior to enrollment. The plan will outline the frequency of monitoring visits based on such factors as study enrollment, data collection status and regulatory obligations.

## 13 Statistical Considerations

### 13.1 Study Hypotheses

This randomized, placebo-controlled, double-blind Phase 2 study followed by an open-label extension is designed to test the hypothesis that benralizumab can safely reduce eosinophilia in patients with HES.

### 13.2 Sample Size Justification

In addition to potentially eligible subjects already followed on protocol 94-I-0079, we receive 1-2 new patient referrals/week for evaluation and treatment of HES. Furthermore, based on prior experience, we anticipate an increase in referrals with the availability of a new clinical trial. Thus, it is likely that recruitment of 20 subjects will be feasible in a 2 year time frame.

The primary endpoint is a binary response (50% reduction in peripheral eosinophil count at 12 weeks). To compare the 2 groups, we will perform a one-sided Fisher's exact test at the 2.5% level (this is essentially the same as a two-sided central Fisher's exact test at the 5% level). For the power calculations, we make some assumptions. First, we assume that we have 10 subjects in each arm of the study. We expect that at 12 weeks virtually none of the subjects randomized to placebo will have a response, so we set that value to 1%. We calculate the power for different levels of response for the subjects on benralizumab. The results are listed in [Table 2](#). Thus, we need 60% responders in the benralizumab group in order to get 79% power to reject at the one-sided 2.5% level (or equivalently at the two-sided 5% level) if we have 10 in each group as planned. If we are only able to recruit 6 in each group by the end of the 2 year accrual, then we need 90% responders to get over 86.4% power.

**Table 2** Power Estimates

Percent Responders	Percent Responders on	Power to Reject (in Percent)	Power to Reject (in Percent)	Power to Reject (in Percent)
--------------------	-----------------------	------------------------------	------------------------------	------------------------------

on Placebo	Benralizumab	N=10 per group	N=8 per group	N=6 per group
1	50	57.9	34.6	10.4
1	60	79.0	57.2	22.2
1	70	92.3	78.5	40.2
1	80	98.2	93.2	63.2
1	90	99.8	99.2	86.4

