tetanus-acellular pertussis (Tdap) booster immunization at the 22 week visit. Titers will be measured 6 weeks after immunization. Subjects with a sustained and complete response to benralizumab with a stable dose for another 2 years will be transitioned to the FasentraPEN autoinjector for at-home self-administration (or by a local provider), with monthly blood counts and visits to the NIH once every 6 months.

**Study Duration:** Start Date: March 2014 End Date: June 2025  
Subjects will be on study for 12 months (or longer if enrolled on the open label extension).

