### 13.3 Description of the Analyses

- **Safety Analysis:** All safety data will be summarized with descriptive statistics (number of subjects [N], mean, standard deviation [SD], median, minimum, and maximum) for continuous variables, and frequency and percentage for discrete variables. The safety summary will include AEs, serious adverse events (SAEs), clinical laboratory data, vital signs, physical examination, and ECG data. All individual subject data will be listed by subject.
- **Efficacy Analysis:** The primary analysis compares the proportion of subjects with a  $\geq 50$  % change in AEC at 12 weeks in the 2 randomized arms. If there is dropout, the primary analysis will be the intent-to-treat analysis, which includes all subjects who received the Day 0 treatment. We will compare with a one-sided Fisher's exact test at the 2.5% level of significance, or equivalently a two-sided central Fisher's exact test at the 5% level.
- For the secondary analysis comparing the 2 groups on the post-treatment AEC at 12 weeks as a percentage of the pre-treatment AEC, we use a Wilcoxon-Mann-Whitney test.
- There are other secondary endpoints with continuous responses that measure a change from pre-treatment to after 12 weeks of treatment: for example, % bone marrow eosinophils, and % bone marrow myeloid precursors. These will be analyzed similarly to the percentage of pretreatment AEC.
- As exploratory analyses, we may use a Mixed-Effect Model Repeated Measure (MMRM) model to analyze changes in AEC over time. The dependent variable will be the percentage of baseline AEC at post-baseline protocol-specified visits (up to the 12 week visit). Treatment group will be fitted as the explanatory variable, together with visit, the interaction between visit and treatment. Visit will be fitted as a categorical variable, and the variance-covariance matrix will be assumed to be unstructured. If the procedure does not converge, then a compound symmetric variance-covariance matrix will be used instead.
- **Calculation or derivation of pharmacokinetic variables**  
The PK analyses will be performed at (or under the guidance of) AstraZeneca Research and Development.

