### **13.4 Final Analysis Plan**

The primary endpoint is the number of subjects with a  $\geq 50\%$  change in AEC. The details of the statistical tests used for this endpoint is described in Section 13.3. For this test and all tests, we define significance using a two-sided 5% level or equivalently a one-sided 2.5% level. If the study shows that there is a significant reduction in AEC, this would merit further study of benralizumab in HES. This design relies on the assumption that the type of HES patients included in this study would not have 50% improvement in their eosinophil count in the absence of a change in therapy. This is a well-established assumption in the HES research community.

This single center trial has 2 parts: 1) a randomized, double-blind comparison of sc benralizumab vs. placebo every 4 weeks for 12 weeks, 2) an open-label extension of sc benralizumab every 4 weeks for 12-36 weeks. The primary endpoint and secondary and exploratory endpoints based on the data from the first part of the study will be analyzed once all 20 subjects have completed the 13 weeks visit and data is unblinded.

Since there are only 20 patients in the study, both an intent-to-treat and a per-protocol analysis may be done. For the intent-to-treat analysis, we will impute a “worst case” post-treatment AEC, whereby we will use the maximum of the baseline AEC or the last AEC as the post-treatment AEC for analysis. If a patient does not complete treatment, that patient may be removed from the per-protocol analysis.

Although we do not specify the exploratory analyses in advance, we do note that care will be taken in making inferences when many analyses are undertaken. If needed multiple comparison adjustments will be made.

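### Does the conservative one-sided Fisher test waste power that Boschloo's test would recover, so that the primary test should be changed?

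*Combined protocol and SAP*

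**What the plan says.** Section 13.2 (Sample Size Justification) defines the outcome: "The primary endpoint is a binary response (50% reduction in peripheral eosinophil count at 12 weeks". It sets placebo response at 1% and tabulates power for benralizumab response of 50% to 90% with 10, 8 or 6 subjects per group. Its summary is that "we need 60% responders in the benralizumab group in order to get 79% power to reject at the one-sided 2.5% level".

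Section 13.3 names the same test, a one-sided Fisher "exact test at the 2.5% level of significance, or equivalently a two-sided central" Fisher test at 5%, and defines the intent-to-treat set as the one "which includes all subjects who received the Day 0 treatment". Section 13.4 adds that for all tests "we define significance using a two-sided 5% level or equivalently a one-sided 2.5% level". It also imputes a missing 12-week count by the larger of the baseline and last counts, so a dropout stays in the denominator as a non-responder.

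On timing, section 11.13.1 states: "The study drug assignments will be unblinded after all 20 subjects have enrolled and completed the 13 week visit". The Protocol Summary gives "Start Date: March 2014 End Date: June 2025" and a 2-year accrual period.

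**The concern.** With 10 per arm, Fisher's p-value takes few distinct values, so a nominal 2.5% test operates well below 2.5%. If no placebo subject responds, as the plan expects, Fisher's test needs 5 benralizumab responders to reject, while Boschloo's test needs 4. In a rare disease with a ceiling of 20 randomised subjects, a test that rejects in every case where Fisher's does, and in some others, looks like power for nothing. The apparent stake is 79.0% against 91.4% power at 60% response, and more if accrual stops at 6 per group (22.2% against 52.6%). Fisher's test would need 12 per arm, four more subjects in all, to reach 91.0%. The plan does not discuss the alternative.

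**Working it through.** **Inputs.** 10, 8 or 6 per group, placebo response 1%, benralizumab response 50% to 90%, one-sided 2.5% (all section 13.2). X is the number of benralizumab responders and Y the number of placebo responders, treated as independent binomials.

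**1. The plan's own figure.** Fisher's one-sided p is the hypergeometric probability of X or more responders on benralizumab given X + Y. At 10 per arm it rejects for X ≥ 5, 7, 8, 9, 10, 10 when Y = 0, 1, 2, 3, 4, 5. At 60% versus 1%:

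- Y = 0: 0.99^10 × P(X ≥ 5) = 0.9044 × 0.8338 = 0.7540
- Y = 1: 10 × 0.01 × 0.99^9 × P(X ≥ 7) = 0.0914 × 0.3823 = 0.0349
- Y ≥ 2: about 0.0007

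The sum is 0.790, the plan's 79%. The other 14 cells of Table 2 also reproduce. The powers are exact for the test named, so the conservatism is already in them.

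**2. Size and power of both tests.** Maximum size is the null rejection probability, maximised over the common response rate. Boschloo's region is the largest set, ordered by Fisher's p, that keeps this at or below 2.5%. Powers are in percent against 1% placebo response.

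| Per arm | Test | Max size | 50% | 60% | 70% | 80% | 90% |
|---|---|---|---|---|---|---|---|
| 10 | Fisher | 0.64% | 57.9 | 79.0 | 92.3 | 98.2 | 99.8 |
| 10 | Boschloo | 2.11% | 78.4 | 91.4 | 97.5 | 99.6 | 100.0 |
| 8 | Fisher | 1.06% | 34.6 | 57.2 | 78.5 | 93.2 | 99.2 |
| 8 | Boschloo | 1.39% | 59.8 | 78.6 | 91.1 | 97.4 | 99.6 |
| 6 | Fisher | 0.32% | 10.4 | 22.2 | 40.2 | 63.2 | 86.4 |
| 6 | Boschloo | 1.93% | 33.0 | 52.6 | 72.5 | 88.6 | 97.8 |

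**3. Where the gain comes from.** At 10 per arm Boschloo's test adds six results (placebo versus benralizumab responders): 0 v 4, 1 v 6, 2 v 7, 3 v 8, 4 v 9 and 6 v 10. At 60% versus 1%, the first has probability 0.9044 × C(10,4) × 0.6^4 × 0.4^6 = 0.9044 × 0.1115 = 0.1008. So about 10.1 of the 12.4 points come from that one result.

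**4. What that result is worth under randomisation.** If treatment had no effect and 4 of the 20 subjects responded, the chance that all 4 had been assigned to benralizumab is C(10,4)/C(20,4) = 210/4845 = 4.33%, above 2.5%. Fisher's boundary case, 5 responders to none, gives C(10,5)/C(20,5) = 252/15504 = 1.63%. Given the total number of responders, the largest rejection rates are:

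| Split | Fisher | Boschloo |
|---|---|---|
| 10/10 | 1.63% | 4.33% |
| 8/8 | 2.03% | 3.85% |
| 6/6 | 0.76% | 4.00% |

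For Boschloo's test this rate reaches 5.13% at 9/10 and 5.21% at 8/12. Fisher's stays at or below 2.5% throughout.

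**5. Dependence on the split.** At 60% versus 1% (placebo/benralizumab), power moves from 79.4% to 81.6% at 9/10 and from 69.4% to 71.3% at 8/9, gains of 2.2 and 1.9 points. At 10/9 it moves from 70.8% to 88.3%, at 9/11 from 73.3% to 86.8%, and at 11/9 from 70.6% to 88.2%. Section 6.3 mentions no blocking. If randomisation were simple (an assumption), a 10/10 split would fail to occur with probability 1 − C(20,10)/2^20 = 1 − 184756/1048576 = 82%.

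**The case for a change.** The case for changing the test is a serious one. Under the binomial model that Table 2 already uses, Boschloo's test keeps the error below 2.5%, and in the splits examined it rejects wherever Fisher's does. The gain falls on the design point that section 13.2 singles out and is largest in the short-accrual case the plan itself considers. It does not hinge on the 1% placebo rate: at 5% placebo and 60% benralizumab response with 10 per arm, power goes from 63.3% to 79.6%. It needs no further subjects or data.

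All of that arithmetic stands, and a team designing this trial could reasonably have chosen Boschloo's test. It does not make Fisher's test a flaw. Fisher's error control follows from the random assignment alone. Boschloo's needs the 20 subjects to behave as independent binomial samples, a stronger assumption for referred patients with what the Précis describes as a heterogeneous group of disorders. Using the binomial model to forecast power is not the same as resting the validity of the primary test on it. Nor is the 60% row an assumed response rate; it is one row of a range. The asthma data in section 1.1.3, with blood eosinophils down by at least 95% by Day 7 in one study, make the upper rows plausible, though HES may differ.

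The change would also be open only before unblinding. The documents do not state the status of the blind. A March 2014 start, 2-year accrual, and the reactions already reported in Appendix D after first open-label doses suggest it may be past. In that case Fisher's test must remain primary anyway.

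**Conclusion.** No defect. The plan names one valid test in sections 13.2, 13.3 and 13.4, at one level, and states its power correctly. Boschloo's test would add 12.4 points at 60% versus 1% response with 10 per arm, but 1.4 points at 80% (98.2% to 99.6%) and 0.2 at 90% (99.8% to 100.0%). The price is a rejection rate, given the total number of responders, of up to 4.33% at 10/10 and above 5% at some uneven splits. Choosing between conditional and unconditional exact inference on those terms is a matter of judgement, and the plan's choice is the one protected by randomisation. The sizes and powers rest on independent binomial responses, with 1% placebo response for the powers except where 5% is stated. The conditional rates rest only on random assignment with the stated arm sizes. The conclusion does not depend on whether the blind has been lifted.
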